9.10 Conclusion regarding non-inferiority

Conclusion on non-inferiority shall be made by the primary efficacy variable using a confidence interval-based approach.

For the primary efficacy variable, the null hypothesis H0 is that the frequency of serious bacterial infection cases is 1.0 or greater per patient per year. The alternative hypothesis H1 is that the frequency of serious bacterial infection cases is less than 1.0 per patient per year. The null hypothesis is rejected if the upper limit of the 99 % confidence interval is less than 1.0 case of serious bacterial infection per patient per year. Then it will be considered that the investigational route of administration of the drug (SCIG manufactured by BIOPHARMA PLASMA LLC) is non-inferior in terms of efficacy compared to the literature data on the level of efficacy of existing SCIG products and compared to the efficacy of BIOVEN use.

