Overall, clinical studies have demonstrated a high efficacy of products of human normal immunoglobulin for subcutaneous administration in both adults [Kanegane H et al. 2014, Ochs

HD et al. 2006, Jolles S et al. 2011] and paediatric patients [Borte M et al. 2011, Sefer AP et al. 2025]. The use of SCIG products in patients with PID was shown to be effective in maintaining infection levels at a very low rate, including a low incidence of serious bacterial infections and overall infection episodes, a reduction in the number of days missed from school/kindergarten or unable to perform usual activities due to infections, the number of days of hospitalisation due to infections, and the use of antibiotics for prevention or treatment of infections [Shrestha P et al., 2019].

2.3 A short description of known and potential risks and benefits, if any, for humans.

A significant proportion of patients prefer subcutaneous administration of immunoglobulin products in the home and are more satisfied with it, primarily due to greater convenience compared with intravenous infusions in a hospital setting [Bril V et al., 2024].

The efficacy and safety of subcutaneous immunoglobulin administration as part of a home-based treatment regimen have been confirmed in numerous prospective, multicentre studies. Indeed, a randomised crossover study (Chapel et al., 2000) demonstrated subcutaneous and intravenous immunoglobulin therapy to be equivalent in terms of efficacy profile and frequency of adverse events. The works by Gardulf et al. (2006, 2008) that included both paediatric and adult patients have demonstrated maintaining sufficient serum IgG levels, low incidence of infections (0.04 severe infections/year) and high treatment compliance with weekly self-administered infusions in the home.

In a paediatric cohort (Borte et al., 2011), the safety of subcutaneous administration of 16 % IgG (Vivaglobin®) in a home-based setting has also been confirmed. No cases of serious bacterial infection were reported during the evaluation period, and the safety profile was similar to that in the adult population.

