4.2. Description of the design

Study design: Open-label, multicentre, single-arm, cohort, uncontrolled, prospective clinical study of tolerability, safety and pharmacokinetics of the medicinal product BP-SCIG 20% for subcutaneous administration with further assessment of efficacy in long-term use.

[figure not shown]

Fig. 1 Study diagram

Number of patients:

56 patients with PID – adults, adolescents, and children.

Patients older than 18 years – at least 20 patients

Patients younger than 18 years – at least 20 patients across different age groups:

- 0 to \leq 2 years – at least 2;
- $>$ 2 to \leq 6 years – at least 4;
- $>$ 6 to \leq 12 years – at least 7;
- $>$ 12 to \leq 18 years – at least 7.

The first 10 patients enrolled in the study must be adults, for an interim safety assessment in adult patients who received at least 4 infusions of the IMP BP-SCIG 20%.

Based on the results of such assessment, the possibility of enrolling patients younger than 18 years of age is determined. The interim report will be reviewed and assessed by the Independent Safety Committee.

In the pharmacokinetic assessment:

- the threshold IgG levels are determined in at least 40 patients, at least 20 of whom must be children and adolescents before the age of 18 years.
- pharmacokinetic parameters (AUC, Cmax, Tmax, $T_{1/2}$, K_{el} , Cl, IR, Vd) are determined in no less than 20 adult patients
- confirmation of the dose adjustment factor (adult patients of cohort B)

Groups:

This study does not involve the distribution of patients into groups. Of patients in all age categories who meet inclusion criteria and passed the screening, and who do not meet any of the non-inclusion (exclusion) criteria, one group is formed, which will receive the investigational product.

The following cohorts are formed from the general group to assess pharmacokinetics:

Cohort A: the patients who have already received subcutaneous immunoglobulin (SCIG);

Cohort B: the patients who previously received intravenous IgG IVIG; **Cohort C:** newly identified patients who have not received treatment with IgG product yet.

Also, PK assessment subgroups are formed from the general group of patients to determine threshold IgG levels (in at least 40 patients, at least 20 of whom must be children and adolescents younger than 18 years), to determine pharmacokinetic parameters (at least 20 adults), and to confirm the dose adjustment factor (adult patients previously receiving BIOVEN).

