9.3 General plan of statistical analysis

General principles of statistical analysis

All continuous variables will be summarised using descriptive statistics and represented as absolute numbers, sample size, arithmetic mean, standard deviation, median and percentiles, minimum and maximum values (depending on the type of distribution). The data on 3OT and on AR frequency will be presented as percentages of the entire population of patients enrolled in the study.

No inferential statistical analysis is planned as part of this uncontrolled study, since the design does not provide for comparison groups. The statistical analysis of the endpoints will be descriptive with testing of the null hypothesis, except for the statistical analysis of PK parameters, which will be compared with the pre-dose and post-dose values in several time intervals.

The source data are presented as tables, with individual study subjects listed in the rows and the values of the characteristic under investigation listed in the columns.

If the measured value of the characteristic under analysis in an individual study subject equals zero, the corresponding cell of the table shall contain the digit “0”.

All statistical calculations will be performed using the software package for statistical analysis R ver. 4.5.0 (2025-04-11 ucrt) and RStudio ver. 2025.05.1 “Mariposa Orchid”.

After study completion (after the last subject completes the study), a final statistical analysis of the results obtained is performed.

Analysis of baseline plan of the group

Perform analysis of the group by clinical and demographic parameters at the time of inclusion in the study. Use the methods of descriptive statistics to describe the baseline state in groups (for

quantitative parameters – n, arithmetic mean, median, standard deviation, minimum and maximum value; for categorical parameters – number and percentage).

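### Section 9.10 turns a single-arm test of an SBI rate below 1.0 per patient-year into a claim of non-inferior efficacy to literature SCIG and to BIOVEN, which the test cannot support

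*Protocol*

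**What the plan says.** Section 9.10 of the protocol opens with: "Conclusion on non-inferiority shall be made by the primary efficacy variable using a confidence interval-based approach". It sets the null hypothesis as an SBI rate of 1.0 or more per patient per year and rejects it when the upper 99% confidence limit is below 1.0. On rejection, the product is to be taken as non-inferior in "efficacy compared to the literature data on the level of efficacy of existing SCIG products and compared to the efficacy of BIOVEN use".

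Other sections bear on whether that follows:

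- **Design (4.2).** The study is described as "Open-label, multicentre, single-arm, cohort, uncontrolled, prospective clinical study of tolerability, safety and pharmacokinetics". All patients form one treated group. It includes Cohort C, "newly identified patients who have not received treatment with IgG product yet".
- **General analysis plan (9.3).** No inferential analysis is planned, "since the design does not provide for comparison groups". The same paragraph adds: "The statistical analysis of the endpoints will be descriptive with testing of the null hypothesis".
- **Objectives (3).** Non-inferiority is stated for steady-state AUC of total IgG against BIOVEN, and for trough IgG against previous therapy (or against the literature in treatment-naïve patients). It is not stated for infections.
- **Eligibility (5.1 criterion 6, 5.2 criterion 14).** Patients with SBIs on the previous product in the 3 months before inclusion, or during screening, are not enrolled.

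**The concern.** Rejecting the null in 9.10 supports one statement: the SBI rate on BP-SCIG 20% is below 1.0 per patient-year. Non-inferiority to a named product is a different statement. It needs a rate for that product and a margin saying how much worse is acceptable. Section 9.10 supplies neither, and it does not derive 1.0 from the rate on any product. The protocol as shown gives no SBI rate on BIOVEN.

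This is a fixed decision rule, not a detail left for later. An analysis plan that follows the protocol would inherit it, and the report of a Phase III study would state non-inferior efficacy to BIOVEN and to existing SCIG products at any SBI rate that passes the benchmark, whatever the rate on those products is.

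**Working it through.** **1. The plan's own figure.** Section 9.2 states at least 80% power with more than 40 patients, one-tailed, at a significance level of 0.01. It gives no assumed true rate, so this can be checked only conditionally. For T patient-years and x events, the exact Poisson upper limit is

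U(x) = χ²(q; 2(x+1)) / (2T),

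with q = 0.99 for a one-sided 99% limit and q = 0.995 for the upper end of a two-sided 99% interval. The plan combines a one-tailed test with a 99% interval, so both are shown. The probability of passing at true rate λ is P(X ≤ c), where X is Poisson with mean Tλ and c is the largest x with U(x) < 1.0. At T = 40, 80% power is reached at a true rate of 0.54 (one-sided) or 0.52 (two-sided). The stated power is therefore plausible for a true rate of about 0.5 or lower, and the test against 1.0 is coherent.

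**2. What the rule accepts.** One patient-year per patient (52 weeks of treatment), no overdispersion.

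| Patient-years | Limit | Most SBIs that pass | Observed rate | U at that count | U with one more |
|---|---|---|---|---|---|
| 40 | two-sided 99% | 24 | 24/40 = 0.600 | 0.994 | 1.025 |
| 40 | one-sided 99% | 25 | 25/40 = 0.625 | 0.983 | 1.013 |
| 56 | two-sided 99% | 37 | 37/56 = 0.661 | 0.995 | 1.017 |
| 56 | one-sided 99% | 38 | 38/56 = 0.679 | 0.982 | 1.003 |

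**3. How often the sentence would be triggered.** The true rates of 0.4 to 0.6 are assumptions. Entries are two-sided / one-sided.

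| True SBI rate per year | 40 patient-years | 56 patient-years |
|---|---|---|
| 0.4 | 0.978 / 0.987 | 0.998 / 0.999 |
| 0.5 | 0.843 / 0.888 | 0.959 / 0.972 |
| 0.6 | 0.554 / 0.632 | 0.754 / 0.803 |
| 1.0 | 0.004 / 0.008 | 0.005 / 0.007 |

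The last row confirms that the test controls its error against 1.0. The other rows show that it does not address the distance from any comparator.

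**4. Against the only literature figures in the protocol.** Section 2.3 cites "low incidence of infections (0.04 severe infections/year" from SCIG studies and, for a paediatric cohort, "No cases of serious bacterial infection were reported during the evaluation period". The first is worded as severe infections and may not match the protocol's SBI definition. Taken at face value, 0.625/0.04 = 15.6 and 0.679/0.04 = 17.0, so a product with an observed rate about 16 or 17 times that figure would be declared non-inferior. The ratio is illustrative, and the finding does not depend on it.

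**5. Can the trial supply the comparator itself?** Not without bias. Being free of recent SBIs on the previous product is a condition of entry, and Cohort C has no previous IgG product.

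**The case against.** The strongest defence is that 1.0 per patient-year is the benchmark the protocol takes from the European SCIG guideline (9.2, 9.4), and that pass or fail on the primary variable is the same with or without the last sentence of 9.10. That is right. A reader might infer from 9.3 that the test itself is out of place in an uncontrolled study, but 9.3 expressly provides for testing the null hypothesis. Only the conclusion attached to it fails. That 9.3 already says there are no comparison groups does not rescue 9.10; it makes the two sections disagree.

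It is also fair that nothing in the protocol points to a true rate of 0.4 to 0.6. The rates cited in 2.3 are far lower, and eligibility removes patients with recent SBIs. A reader might take the tables as predicting a misleading report. They do not: they show what the rule would let through. The 56 patient-year figures further assume no loss, although 56 was chosen to allow for withdrawals and the main efficacy analysis (9.1) is per protocol.

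The Cohort C remark bears on the comparison with BIOVEN as a previous therapy. By itself it does not undermine the literature comparison.

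A wider reading is that the protocol has no rule for its pharmacokinetic non-inferiority objectives. The document does not support that for trough IgG. Section 4.1 requires monthly troughs not to fall below those on previous therapy, section 3 adds a criterion of at least 5 g/L, and 4.2 and 9.6 fix the comparator (at least two prior infusions) and the window (after 4 months, every 4 weeks, over 6 months). A numerical margin for AUC is commonly left to the statistical analysis plan, which is not shown.

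**Conclusion.** The conclusion in 9.10 is wrong as written. The test can establish an SBI rate below 1.0 per patient-year, but it cannot establish non-inferior efficacy to literature SCIG or to BIOVEN. This rests on the text alone: one arm, no comparison groups, no comparator rate or margin, and entry conditions that rule out an unbiased prior-therapy rate.

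Its size, under exact Poisson counts with one year per patient and no overdispersion, is that observed rates up to 0.60–0.68 per year still yield the claim. At an assumed true rate of 0.5 the claim follows in 84–89% (40 patient-years) or 96–97% (56) of trials. The benchmark test, its threshold and the sample size are not in question.

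One subordinate remark: 9.10 ties the non-inferiority conclusion to the SBI variable, while section 3 states non-inferiority for AUC and trough IgG. The two should not be run together.

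**What to change.** **Main change, in 9.10.** Limit the conclusion to an SBI rate below 1.0 per patient-year, reword the heading and opening sentence to match, and delete the non-inferiority wording about literature SCIG and BIOVEN. Report any comparison with either descriptively.

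The cost is a few lines of text. The test, threshold, sample size, procedures and data collection do not change; the efficacy claim becomes narrower. Keeping a true non-inferiority claim would instead need a sourced comparator rate and a justified margin, and the study would have to be sized for it. With an assumed true rate of 0.04, a one-sided 0.01 level and 80% power, showing a rate below 0.20 takes about 51 patient-years, and below 0.10 about 202.

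**Subordinate change.** Separate the pharmacokinetic objectives of section 3 from the SBI conclusion. Reconcile the trough criterion in 4.1 (monthly levels not falling below the previous ones) with objective 3 and with the mean-trough endpoint, so that one criterion applies. Standardise any AUC comparison for dosing interval, since sampling covers 7 days on the study product and 21–28 days on BIOVEN (Tables 4.2.2 and 4.2.3). This is wording only.

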9.11 Analysis dataset

ITT (Intention-to-treat population) includes all study subjects who received the investigational product at least once. The data obtained from this sample will be used for the safety analysis.

PP (Per Protocol) includes all patients who complied with the protocol requirements. This population includes all patients who received full protocol therapy, who underwent all scheduled visits, and did not have significant protocol deviations. The data obtained from this sample will be used for analysis by efficacy criteria.

9.12 Final presentation of results

The results of statistical analysis of the obtained findings shall be presented in the form of tables, which, if necessary, are illustrated by graphs and diagrams. Data presentation shall be structured in accordance with the purpose and objectives of the CS. It is necessary to clearly indicate the methods used, to characterise the data set.

10. DIRECT ACCESS TO SOURCE DOCUMENTS

Source data include all information contained in the original records and/or certified copies of clinical data, observations and other activities within the study, and which is necessary for the reconstruction and evaluation of the study. The Investigator ensures the possibility of conducting study monitoring and audit(s), expert assessment by IEC and regulatory authorities, and provides direct access to source data/records to the representatives of the aforementioned bodies.

Source data shall be stored for a maximum period of time permitted by local regulations, but for no less than 25 years after CT completion and archiving. For each enrolled subject, the Investigator shall indicate the fact of participation in this study in the source records, and shall record at least the following information: individual screening number, patients' personal data (full name, address), dates of drug administration, vital signs, any AEs, study completion dates and main reasons for treatment discontinuation (if any), etc.

It is the Investigator's responsibility to ensure direct access to source data and documents for the clinical study specialist of the Sponsor and/or its authorised representatives (CRO), the auditor of competent authorities, the representatives of the insurance company, independent ethics committees or other organisations according to the current legislation.

11. QUALITY CONTROL AND QUALITY ASSURANCE

11.1. Study monitoring

Regular visits by the Study Monitor, as requested by the Sponsor and according to standard operating procedures (SOPs), before the onset of the study, during the study and after the end of the study contribute to successful completion of the trial, and serve as a guarantee of accurate data collection, timely identification of potential errors, documenting the process of the clinical trial and ensuring the protection of rights of study subjects, as well as the compliance of the study conduct with the requirements of Ukrainian legislation.

Routine monitoring of the study includes the following:

- confirmation of proper conduct and documenting of the informed consent process as well as screening and subject enrolment;
- verification of data in the eCRF and their compliance with source medical records of study subjects;
- verification of completion of patient's diary (PD) and source medical records of study subjects;
- confirming adherence of clinical site personnel to the protocol-specified requirements for diagnostic tests and therapeutic interventions;
- confirmation of documented supplies, storage, distribution and disposal of the investigational medicinal product and study materials;
- confirming the competencies of personnel of the clinical site and the external laboratory, which are essential for study conduct;
- confirming the compliance of diagnostic and laboratory equipment to the requirements of safe and appropriate use during the study;
- confirming the interactions of the Investigator with the Independent Ethics Committee concerning study safety and making Sponsor-approved amendments to the Study Protocol. Quality control assurance of study results is carried out by the employees of the Sponsor/employees of Sponsor's authorised representative (e.g., the CRO) who maintain the database of the study and detect inconsistencies, erroneous data entries and missing data. In the event of questions or a need for clarification, an inquiry is sent to the Investigator by e-mail, to which a written response must be provided within 7 days of receipt.

As required by law, the Sponsor or authorised public authorities have the right to conduct an inspection (audit) of material and technical support and documentation of the study. The Investigator must provide the persons authorised to perform audits or inspections with access to documentation and to all required information.

11.2. Amendments to the protocol, deviations from and violations of the protocol

The signatures of investigators on the signature page of the Protocol constitute a written confirmation of their agreement to conduct the study according to this Protocol and the regulatory and legal requirements to CT conduct. During conduct of the clinical study, changes and additions can be made to study materials. Such changes and additions shall be viewed as amendments.

Amendments to the clinical study materials are considered substantial if they may affect the goals, forms of organisation, methodology, and statistical methods for processing the clinical study results. Amendments to the protocol shall be stored with the initial version of the protocol.

Any changes shall be agreed upon between the Investigator and the Sponsor prior to their coming into force. Any changes to the study conduct that occurred after the protocol was approved must be documented as alterations to the protocol and/or as an updated version of the protocol. Depending on the nature of the amendment, an approval by or notification of the IEC and regulatory authorities will be required, except when there is an immediate threat to the life or health of patients participating in the clinical study, or when changes to the protocol concern only administrative aspects or supply issues.

All deviations from the protocol occurring during the study must be documented and checked during monitoring of the clinical study and reported to the Sponsor.

The investigator shall not deviate from the protocol, except where it is necessary to exclude a serious risk to the health of patients in the study. If there are other unexpected circumstances that require deviation from the protocol-defined procedures, the Investigator must seek consultation with the Sponsor or its representative (and IEC if required) to determine an appropriate procedure.

The study site shall document all deviations from the protocol in patients' source documentation. In the event of a substantial deviation, the Investigator must notify the Sponsor or its representative (and IEC if required). To do this, the Investigator shall complete the "Protocol Deviations" form, which is sent by email to the Sponsor. During the monitoring of the CTS, the Monitor may identify deviations from the Study Protocol. In this case, he/she is responsible for notifying the investigators about the identified deviations and for preparing the "Protocol Deviations" form.

Deviations from the Protocol can be divided into substantial and non-substantial.

Substantial deviations include, but are not limited to, those deviations that include document forgery or improper conduct of the study, increase the risk to the patient's health, or confound the analysis of the main study results.

Examples of such deviations are given below.

Substantial deviations from the protocol:

- 1) unsigned/incorrectly signed Patient Informed Consent to participate in the clinical study;
- 2) deviation from patient inclusion/non-inclusion criteria;
- 3) significant deviation from the Schedule of Study Procedures (deviation from the list of protocol-specified procedures);
- 4) significant deviation from the schedule of therapy of patients (inconsistency with the Protocol-specified therapy);
- 5) unreasonable disclosure of a patient's personal data and failure to notify the Sponsor of such disclosure;
- 6) failure to report (concealment of information) about a serious adverse event that occurred in a patient during the study;

- 7) failure to comply with the IMP storage conditions.
- 8) untimely (with delay) notification of an SAE;

Non-substantial deviations from the protocol:

- 1) violation of the Schedule of Study Procedures on the visit days, which slightly exceeds the time-frames provided by the Protocol;
- 2) untimely entering of data in the eCRF;
- 3) other unexpected deviations that do not pose a threat to patient safety.

All deviations from the Protocol occurring during the study must be documented during the monitoring of the clinical study and reported to Sponsor.

11.3. Audits by quality control bodies and regulatory authorities.

During any phase of CT conduct, the Sponsor can conduct a CT audit at the clinical trial site to verify and ensure the quality of CT conduct. In the first case, a Sponsor-appointed auditor will contact the Investigator in advance to arrange a visit for the purpose of conducting an audit. The auditor has the right to inspect the place where laboratory samples are collected, where the medicinal product is stored, and any other place used during the study, including verification of source medical documentation.

In the event of knowledge about a scheduled conduct of a clinical audit/inspection by representatives of regulatory authorities of Ukraine or other countries, the Investigator must immediately inform the Sponsor about it.

